6.2 Study Intervention(s) Preparation, Handling, Storage, and Accountability

Further guidance and information for the preparation, handling, and storage of study intervention(s) are provided in the Pharmacy Manual.

The Investigator, institution, or the head of the medical institution (where applicable) is responsible for study intervention accountability, reconciliation, and record maintenance (i.e, receipt, reconciliation, and final disposition records).

- Upon receipt of the study intervention(s), the Investigator or designee must confirm appropriate temperature conditions have been maintained during transit and any discrepancies are reported and resolved before use. Also, the responsible person will check for accurate delivery and acknowledge receipt by signing or initialing and dating the appropriate document and returning it to the location specified. A copy will be archived for the Investigator Site File.
- Only participants enrolled in the study may receive study intervention(s) and only authorized site staff may supply or administer it. All study intervention(s) must be stored in a secure, environmentally-controlled, and monitored (manual or automated) area, in accordance with the labeled storage conditions, and with access limited to the Investigator and authorized site staff.
- Dispensing will be recorded on the appropriate accountability forms so that accurate records will be available for verification at each monitoring visit.
- Study intervention(s) accountability records at the study site will include the following:
 - Confirmation of receipt, in good condition and in the defined temperature range.
 - The inventory provided for the clinical study and prepared at the site.
 - The dose(s) each participant used during the study.
 - The disposition (including return, if applicable) of any unused study intervention(s).
 - Dates, quantities, batch numbers, container numbers, expiry dates, formulation (for study interventions prepared at the site), and the participant numbers.
- The Investigator site will maintain records, which adequately documents that participants were provided the doses specified in this protocol, and all study intervention(s) provided were fully reconciled.
- Unused study intervention(s) must not be discarded or used for any purpose other than the present study. No study intervention that is dispensed to a participant may be re-dispensed to a different participant.
- A Study Monitor will periodically collect the study intervention(s) accountability forms.
- Destruction of used and unused study intervention(s) should be performed at site if allowed by local law only after Sponsor authorization. If that is not possible, the Sponsor/designee will be responsible.
- Further guidance and information for the final disposition of unused study intervention(s) are provided in the Pharmacy Manual.

6.2.1 M7824

M7824 drug product should be CCI until use. CCI

Additional instructions for the preparation, handling, storage, and disposal of M7824 will be provided in the Pharmacy Manual.

6.2.2 Pembrolizumab

Pembrolizumab drug product should be CCI CCI CCI

CCI CCI

Additional instructions for the preparation, handling, storage, and disposal of pembrolizumab will be provided in the Pharmacy Manual.

6.3 Measures to Minimize Bias: Study Intervention Assignment and Blinding

6.3.1 Study Intervention Assignment

Participants will be randomly assigned to treatment in a 1:1 ratio to minimize bias. The randomization will be stratified by squamous histology, nonsquamous histology and never smoked, and nonsquamous histology with a smoking history. Once a participant meets the eligibility criteria, is confirmed, and is enrolled, the participant will be randomly assigned to a unique randomization number that is associated with the treatment assignment per the randomization schedule.

Participant identifiers will comprise 17 digits, the first 10 digits representing the study number, the following 3 digits representing the site number, and the last 4 digits representing the participant number, which is allocated sequentially starting with 0001.

After confirmation of participant's eligibility and at the last practical moment prior to study intervention administration, participants will be centrally allocated to either M7824 or pembrolizumab in a 1:1 ratio using an Interactive Web Response System (IWRS) and per a computer-generated randomization list.

The IWRS will be used to assign unique participant numbers, allocate participants to study intervention group at the randomization visit, and study intervention to participants at each study intervention visit.

Before the study is initiated, the IWRS will be provided to each site. The site will contact the IWRS prior to starting study intervention administration for each participant.

6.3.2 Blinding

This is an open-label study; thus, study intervention is not blinded to participants or Investigators.

The IRC will be blinded to a participant's study intervention during their efficacy assessments.

The study team is blinded for all analyses conducted by treatment arm until the IDMC recommends unblinding.

6.4 Study Intervention Compliance

In this study, participants will receive study intervention at the investigational site. Well-trained medical staff will monitor and perform the study intervention administration. The information of each administration including the date, time, and dose of study intervention will be recorded on the electronic case report form (eCRF). The Investigator will make sure that the information entered into the eCRF regarding study intervention administration is accurate for each participant. Any reason for nonadherence should be documented.

Nonadherence is defined as a participant missing study intervention for nonmedical reasons and barring any extenuating circumstances in the opinion of the Investigator. Extenuating circumstances should be documented, and when possible, discussed with the Sponsor in advance. If the interval between the subsequent treatment cycle and the last administered treatment cycle is longer than 6 weeks for nonmedical reasons, the criterion for insufficient adherence is met as well.

Consequences of noncompliance may lead to discontinuation of study interventions as described in Section 7.1. In case of overdose, see Section 8.4.

6.5 Concomitant Therapy

Record in the eCRF all concomitant therapies (e.g., medicines or nondrug interventions) used from the time the participant signs the main informed consent until completion of the study, including any changes. For prescription and over-the-counter medicines, vaccines, vitamins, and herbal supplements, record the name, reason for use, dates administered, and dosing information.

Contact the Medical Monitor for any questions on concomitant or prior therapy.

6.5.1 Permitted Medicines

The only permitted medications are the following:

1. Any medications (other than those excluded by the exclusion criteria or the prohibited medicines) that are considered necessary for the participants' welfare and will not interfere with the study intervention may be given at the Investigator's discretion.
2. Other drugs to be used for prophylaxis, treatment of hypersensitivity reactions, and treatment of fever or flu-like symptoms are described in Section 6.9 as part of precautions

Any medicines that are considered necessary to protect the participant's welfare in emergencies may be given at the Investigator's discretion, regardless if it results in a protocol deviation. The Medical Monitor must be contacted if a drug listed under the exclusion criteria was given, but the Investigator would like the participant to be considered for continuation on study.

6.5.2 Prohibited Medicines

As stated for the exclusion criteria in Section 5, participants must not have had prior systemic cytotoxic chemotherapy for their metastatic NSCLC OR any antibody or drug targeting T-cell coregulatory proteins (immune checkpoints) such as anti-PD-1, anti-PD-L1, or anti-CTLA-4 antibody OR concurrent anticancer treatment including:

- Cytoreductive therapy
- Radiotherapy delivered for non-palliative indications (see Section 6.5.3)
- Use of any investigational drug as specified in Section 1.3 (Schedule of Activities).
- Immunotherapy, immunosuppressive drugs (i.e., chemotherapy or systemic corticosteroids except for short-term treatment of allergic reactions or for the treatment of irAEs), or other experimental pharmaceutical products. Short-term administration of systemic steroid (i.e., for allergic reactions or the management of irAEs is allowed).
- Vaccine administration within 30 days before M7824 or pembrolizumab administration. Vaccination with live vaccines while on study is prohibited. Administration of inactivated vaccines is allowed (e.g., inactivated influenza vaccines).
- Any traditional Chinese medication or herbal equivalent with approval for use as anticancer treatment (regardless of the type of cancer) will not be permitted. Traditional Chinese medication for indications other than anticancer treatment, such as supportive care, may be administered at the discretion of the Investigator (see Appendix 4).

If the administration of a nonpermitted concomitant drug becomes necessary during the study, the participant will be withdrawn from study intervention (the Sponsor may be contacted to discuss whether there is a possibility for a participant to continue on study). The participant should complete the End-of-Treatment Visit and be followed for survival.

6.5.3 Permitted/Prohibited Procedures

Permitted Procedures

Organ-sparing radiotherapy may be administered for palliative and/or specific clinical indications during the study. The assessment of PD will be made according to RECIST 1.1 and not based on the necessity for palliative radiotherapy. The indication for palliative radiotherapy must be documented and discussed with Medical Monitor, in advance of procedure if clinically feasible.

Prohibited Procedures

The following nondrug therapies must not be administered during the study (or within 28 days before randomization):

-
- Major surgery (excluding prior diagnostic biopsy) within 4 weeks before the start of the study. Discuss with Medical Monitor if unplanned major surgery is required on study to plan for timing of next dose.

6.5.4 Other Interventions

The following nondrug therapies must not be administered during the study:

- Herbal remedies with immunostimulating properties (e.g., mistletoe extract) or known to potentially interfere with major organ function (for example, hypericin).

6.6 Dose Selection and Modification

See Section 4.3 for the justification of doses used in this study.

Doses cannot be delayed beyond the treatment window. Participants must skip dose if the treatment window is missed. Every attempt should be made to perform applicable assessments in Table 1 and Table 2 for any missed visits. Complete the next visit following the schedule of assessments.

6.7 Study Intervention After the End of the Study

After a participant has completed the study or has withdrawn early, participants may receive the care they and their physicians agree upon. Participants will be followed for survival and AEs as specified in Section 4.1.

6.8 Special Precautions

6.8.1 Specific Planned Assessments

6.8.1.1 Adverse Events of Special Interest/Identified Risks

See Section 6.9 for AESIs and risk management.

6.8.1.2 Additional Potential Risks

Alterations in Wound Healing or Repair of Tissue Damage

Due to the involvement of TGF β in tissue and skin repair, alterations in wound healing or repair of tissue damage is considered an important potential risk. No relevant event is reported in the ongoing M7824 clinical studies. Monitoring of any surgical wounds while on study is recommended. In general, a 2-week delay from treatment is recommend following minor surgery and 4 week delay for major surgery, but cases should be discussed with the Medical Monitor.

Embryo-fetal Toxicities

Embryo-fetal toxicities are a known risk of the PD-1/PD-L1 targeting class. Animal models link the PD-1/PD-L1 signaling pathway with maintenance of pregnancy through induction of maternal immune tolerance to fetal tissue (Guleria, 2005; Leber, 2010; Wafula, 2009; Zenclussen, 2013).

Embryo-fetal and reproductive toxicities have also been investigated in animal models for a humanized monoclonal antibody targeting TGF β 1. At doses as high as 30 mg/kg, no maternal reproductive toxicity or embryo-fetal lethality were observed in rabbits (Hilbish, 2016). To mitigate these potential risks, pregnant participants are excluded from the study, and all participants of childbearing/conceiving potential must use highly effective contraception.

6.8.2 Adverse Drug Reactions Requiring Treatment Discontinuation

Adverse drug reactions are defined in this study as any AEs related to study intervention assessed by the Investigator and/or Sponsor. Serious adverse reactions are ADRs which are assessed as serious. Any questions or concerns with regards to management and/or follow-up of ADRs should be discussed with the Medical Monitor.

Immune-related AEs, IRRs including hypersensitivity, anemia, TGF β -mediated skin reactions, and bleeding events are managed and followed-up in their respective sections as indicated below. Permanent Treatment discontinuation may be recommended, so the relevant section must be reviewed:

- For management and guidance of suspected irAEs, see Section 6.9.2.
- For infusion-related reactions and hypersensitivity reactions guidance, see Section 6.9.1.
- For anemia guidance, see Section 6.9.4.
- For guidance and management for potentially TGF β mediated skin AEs, see Section 6.9.3
- For guidance and management of bleeding events, see Section 6.9.5.

General guidance:

- In any case, if ≥ 2 doses are missed due to AE, the Medical Monitor should be consulted.
- Inability to reduce corticosteroid dose to 10 mg or less of prednisone or equivalent per day within 12 weeks is an indication for permanent treatment **discontinuation** (except for use of steroids as hormone substitution).
- Persistent Grade 2 or 3 adverse reactions (excluding endocrinopathies controlled with hormone replacement therapy) that do not recover to Grade ≤ 1 within 12 weeks after last dose of study intervention is an indication for permanent treatment discontinuation.

Grade 4 ADRs:

- Participants with Any Grade 4 ADRs require permanent treatment discontinuation except:
 - a. Isolated laboratory values out of normal range that do not have any clinical correlation. Discuss with Medical Monitor regarding work-up, management, and treatment continuation versus hold versus discontinuation for isolated Grade 4 laboratory abnormalities.
 - b. Endocrinopathies controlled with hormone replacement therapy.
 - c. If alternative explanation is identified for Grade 4 non-tumor bleeding.

See Section 6.9.2 for other suspected Grade 4 irAEs, as most require permanent treatment discontinuation.

Grade 3 ADRs:

1. Participants with any severe or Grade 3 treatment-related adverse reactions that recur should be permanently discontinued. Exceptions may be considered as follows after discussion with Medical Monitor:
 - a. Transient (≤ 6 hours) Grade 3 flu-like symptoms or fever, which is controlled with medical management.
 - b. Transient (≤ 24 hours) Grade 3 fatigue, local reactions, headache, nausea, emesis that resolves to \leq Grade 1 or baseline.
 - c. Tumor flare phenomenon defined as local pain, irritation, or rash localized at sites of known or suspected tumor.
 - d. Grade 3 hemoglobin decrease (< 8.0 g/dL) that is clinically manageable with blood transfusions or erythroid growth factor.
 - e. Increases in ECOG PS ≥ 3 that resolves to ≤ 2 by Day 1 of the next infusion (i.e., infusions should not be given if the ECOG PS is ≥ 3 on the day of treatment and should be delayed until ECOG PS ≤ 2).
 - f. Keratoacanthomas and/or cSCC (see Section 6.9.3 for management).
 - g. Grade 3 non-tumor bleeding requiring intervention or hospitalization if alternative explanation can be identified (such as concomitant use of antithrombotic agents, traumatic event, etc).
2. See Section 6.9.2 for suspected Grade 3 irAEs as many require permanent treatment discontinuation, including pneumonitis and nephritis.
 - a. AST or ALT > 5 times ULN or total bilirubin greater than 3 times ULN must be permanently discontinued, *except* for participants with liver metastases (for example) who begin treatment with Grade 2 AST or ALT. These participants should be discontinued if AST or ALT increases by $\geq 50\%$ relative to baseline and lasts for at least 1 week.
3. Persistent Grade 3 adverse reactions (excluding endocrinopathies controlled with hormone replacement therapy) that do not recover to Grade ≤ 1 within 12 weeks after dose of treatment.

Grade 2 ADRs should be managed as follows:

- If a Grade 2 ADR resolves to Grade ≤ 1 by the day before the next infusion, treatment may continue.
- If a Grade 2 ADR does not resolve to Grade ≤ 1 by the day before the next infusion, but it is manageable and/or not clinically relevant, the Medical Monitor should be consulted to assess if clinically reasonable to administer the following infusion.

6.9 Management of Adverse Events of Special Interest

As a part of precautionary safety measures, a risk management guidance is defined for both treatment arms (M7824 and pembrolizumab) for IRRs and irAEs, which may arise on either arm due to the common mAb inhibition of PD-L1.

6.9.1 Infusion-related Reactions Including Immediate Hypersensitivity

Infusion-related reactions, including hypersensitivity, are defined in this section. Infusion-related reactions are AESIs and identified risks for M7824.

Infusion-related reactions are defined as any signs or symptoms experienced by participants occurring during or within 1 day of study intervention administration. An assessment for possible IRR should be triggered based upon the development of specific symptoms within 24 hours of an infusion.

These possible IRRs are identified based on a list of Medical Dictionary for Regulatory Activities (MedDRA) preferred terms and criteria based on the timely relationship to an infusion. Events are divided into reactions versus signs and symptoms:

- Infusion-related reactions should be considered when onset is on the day of infusion (during or after the infusion) or the day after the infusion (irrespective of resolution date) for infusion-related reaction, drug hypersensitivity, anaphylactic reaction, hypersensitivity, and Type 1 hypersensitivity.
- Signs and symptoms of IRRs and hypersensitivity/allergic reactions should be considered when onset is on the day of infusion (during or after the infusion) and resolved completely with the end date within 2 days after onset of (but not limited to) pyrexia, chills, flushing, hypotension, dyspnea, wheezing, back pain, abdominal pain, and urticaria.

Management of Infusion-Related Reactions

Current experience in more than 700 study participants revealed that IRRs to M7824 occur seldomly and are generally mild to moderate in severity. Therefore, administration of a premedication is generally not required.

If an investigator deems necessary to administer a premedication to a particular participant, an antihistamine (e.g. 25 to 50 mg diphenhydramine) and paracetamol (acetaminophen, 500 to 650 mg iv or equivalent oral dose) 30 to 60 minutes prior to M7824 infusion is recommended. Premedication should be administered for subsequent M7824 doses based upon clinical judgment and presence/severity of prior infusion reactions. This regimen may be modified based on local

treatment standards and guidelines as appropriate, provided it does not include systemic corticosteroids.

Table 8 Treatment Modification for Symptoms of Infusion-related Reactions

NCI-CTCAE v5.0 Grade	Treatment Modification
Grade 1 – mild Mild transient reaction; infusion interruption not indicated; intervention not indicated.	Increased monitoring of vital signs as medically indicated, presuming these participants are deemed medically stable.
Grade 2 – moderate Therapy or infusion interruption indicated but if responds promptly to symptomatic treatment (for example, antihistamines, NSAIDs, narcotics, IV fluids); prophylactic medications indicated for ≤ 24 hours.	Stop M7824/ Pembrolizumab infusion. Increased monitoring of vital signs as medically indicated as participants are deemed medically stable by attending Investigator. If symptoms resolve quickly or decreased to Grade 1, resume infusion at 50% of original rate with close monitoring of any worsening otherwise dosing held until resolution of symptoms with mandated premedication for the next schedule. If worsens to Grade 3 or 4, follow treatment modification guidelines accordingly.
Grade 3 or Grade 4 – severe or life-threatening Grade 3: Prolonged (for example, not rapidly responsive to symptomatic medication and/or brief interruption of infusion); recurrence of symptoms following initial improvement; hospitalization indicated for clinical sequelae. Grade 4: Life-threatening consequences; urgent intervention indicated.	Stop the M7824/Pembrolizumab infusion immediately and disconnect infusion tubing from the participant with additional appropriate medical measures and close monitoring until deemed medically stable by attending Investigator. Hospitalization may be indicated. Participants will be permanently withdrawn immediately from M7824/ Pembrolizumab treatment and must not receive any further M7824/Pembrolizumab treatment
NCI-CTCAE = National Cancer Institute-Common Terminology Criteria for Adverse Event; NSAIDs = nonsteroidal anti-inflammatory drugs. For Grade 3 or 4 infusion-related reactions, M7824/Pembrolizumab discontinuation is mandated. For all types and grades of infusion reactions, details about drug physical constitution, method of preparation and infusion must be recorded.	

In the event of a Grade 2 IRR that does not improve or worsens after implementation of the dose modifications indicated in Table 8 (including reducing the infusion rate by 50%), the Investigator may consider treatment with corticosteroids and the infusion should be stopped for that day. At the next infusion, the Investigator may consider the addition of H2 blocker antihistamines (for example, famotidine or ranitidine), in addition to proposed premedication, for select participants. However, prophylactic steroids are NOT permitted. At next dose, if the participant has a second IRR Grade ≥ 2 on the slower infusion rate, with the addition of further medication to premedication, the infusion should be stopped, and the participant removed from treatment.

Hypersensitivity Reaction

If a hypersensitivity reaction occurs, the participant must be treated according to the best available medical practice. A complete guideline for the emergency treatment of anaphylactic reactions according to the Working Group of the Resuscitation Council (UK) and can be found at <https://www.resus.org.uk/pages/reaction.pdf>. Participants should be instructed to report any delayed reactions to the Investigator immediately.

Symptoms may include, but are not limited to:

- Impaired airway
- Decreased oxygen saturation (< 92%)
- Confusion
- Lethargy
- Hypotension
- Pale/clammy skin
- Cyanosis.

Management of hypersensitivity includes:

1. Epinephrine injection and iv dexamethasone
2. Participant should be placed on cardiac, blood pressure, heart rate, and oxygen saturation monitor immediately
3. Alert intensive care unit for possible transfer if required.

Prophylaxis of flu-like symptoms

For prophylaxis of flu -like symptoms, a nonsteroidal anti-inflammatory drug (NSAID), for example, ibuprofen 400 mg or comparable NSAID dose, may be administered 2 hours before and 8 hours after the start of each IV infusion.

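### Protocol 6.9.1: symptoms that resolve and return at the 50% infusion rate are Grade 3 with mandatory discontinuation in Table 8, but can be read as a re-treatable Grade 2 reaction in the paragraph below it

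*Protocol*

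**What the plan says.** Protocol Section 6.9.1 handles IRRs in both arms through Table 8 and a paragraph directly after it.

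**Table 8, Grade 2.** The definition depends on response: "Therapy or infusion interruption indicated but if responds promptly to symptomatic treatment". The infusion is stopped, and the restart is conditional: "If symptoms resolve quickly or decreased to Grade 1, resume infusion at 50% of original rate with close monitoring of any worsening". If that condition is not met, dosing is held until symptoms have resolved, and premedication is compulsory at the next scheduled dose. The row ends: "If worsens to Grade 3 or 4, follow treatment modification guidelines accordingly".

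**Table 8, Grade 3.** The descriptors are a prolonged reaction, with "not rapidly responsive to symptomatic medication and/or brief interruption of infusion" given as an example; "recurrence of symptoms following initial improvement"; and a need for hospitalization for clinical sequelae. The action for Grade 3 or 4 is permanent withdrawal with no further dosing. The footnote repeats it: "For Grade 3 or 4 infusion-related reactions, M7824/Pembrolizumab discontinuation is mandated".

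**Paragraph below the table.** It opens "In the event of a Grade 2 IRR that does not improve or worsens after implementation of the dose modifications indicated in Table 8" and names the 50% rate reduction as one of those modifications. Corticosteroids may be considered and "the infusion should be stopped for that day". At the next infusion an H2 blocker may be added to the premedication. The participant leaves treatment if a second IRR of Grade 2 or higher then occurs at the slower rate despite the extra premedication.

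**The concern.** The two texts sit next to each other and govern the same bedside decision. If one clinical course satisfies both, a site following the paragraph literally could re-infuse a participant whom Table 8 bars from any further dose. This applies in either arm, because Table 8 names both drugs and the paragraph names neither.

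The stake is participant safety first. IRRs are an adverse event of special interest and an identified risk for M7824. The reporting consequence is secondary: SAP Section 15.2.3.1 tabulates participants whose IRR ended treatment permanently, and that count would depend partly on which text a site applied.

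**Working it through.** No plan figure is at issue and no arithmetic applies. The check follows one clinical course through both texts.

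**Course A: symptoms resolve, then return at half rate.**

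1. A Grade 2 IRR occurs and the infusion is stopped. Both texts agree.
2. Symptoms resolve quickly, so Table 8 allows the restart: "If symptoms resolve quickly or decreased to Grade 1, resume infusion at 50% of original rate with close monitoring of any worsening". A participant running at half rate under this row has already improved, because improvement is the entry condition.
3. Symptoms come back at half rate.
4. Under Table 8 this is "recurrence of symptoms following initial improvement", a Grade 3 descriptor. Further infusions allowed: 0.
5. Under the paragraph this can be read as a Grade 2 IRR that worsened after the rate was halved. The infusion ends for the day and a next infusion is described. Further infusions allowed: at least 1, though not required. Removal waits for a second reaction.

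Steps 4 and 5 cannot both be followed. The conflict comes from the ordering in step 2: the paragraph cites the 50% rate as a modification already applied, and on the day of the reaction Table 8 applies that rate only after improvement.

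**Course B: no improvement after the infusion is stopped.**

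1. Table 8 lists "not rapidly responsive to symptomatic medication and/or brief interruption of infusion" under Grade 3, but as an example of a prolonged reaction, not as a free-standing criterion.
2. The Grade 2 row has its own branch for symptoms that neither resolve quickly nor fall to Grade 1: hold, wait for resolution, premedicate at the next scheduled dose. Table 8 itself therefore allows re-dosing after slow resolution.
3. Section 6.8.2 adds that if a Grade 2 drug reaction has not come down to Grade 1 or less by the day before the next infusion, the Medical Monitor is consulted on whether to dose.

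The paragraph and the Grade 2 row can point the same way here. Course B is not a clear conflict.

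**Which text prevails in course A?**

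- For discontinuation: the escalation line "If worsens to Grade 3 or 4, follow treatment modification guidelines accordingly", the footnote "For Grade 3 or 4 infusion-related reactions, M7824/Pembrolizumab discontinuation is mandated", and the duty in Appendix 6 to grade each event by NCI-CTCAE.
- For re-treatment: the paragraph's own Grade 2 label and its explicit mention of the 50% rate.
- Section 6.8.2 does not decide it. For IRRs it sends the reader back to 6.9.1.

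The weight favours discontinuation, but the paragraph cites Table 8 only for its dose modifications and not for the boundary with Grade 3.

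**The case against.** The strongest reply is that the paragraph limits itself to Grade 2 and operates after Table 8 has been applied, including the escalation line. A reaction that meets a Grade 3 descriptor is no longer Grade 2, so the paragraph never reaches it, and correct grading removes the problem. On that view, worsening means worsening within Grade 2, and the Medical Monitor is available for doubtful cases.

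Much of this stands. It is why the paragraph should not be read as permission to re-treat Grade 3 reactions in general, an inference that a reader might draw and that the escalation line and footnote contradict. What does not stand is that the text makes the limit plain. The paragraph attaches the Grade 2 label itself, so a site that accepts the label has no prompt to go back to the escalation line or to call the Medical Monitor.

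A reader might also infer that a reaction that fails to improve is a second contradiction. The documents do not support that, for the reasons given under course B.

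On consequence, the reply is fair that the effect is small. Section 6.9.1 says that IRRs occur seldom with M7824 and are mostly mild to moderate. SAP Section 6.6 records that the sponsor decided to discontinue the study, which limits future exposure. That lowers the priority without removing the point: Protocol Version 4.0 is dated 22 June 2021, after the SAP version of 22 April 2021 that added the post-discontinuation analyses. It keeps both dosing schedules, and its change summary lists a clarification of this same section.

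**Conclusion.** The point holds for one course: symptoms that resolve and then return at the 50% rate. Table 8 ends treatment, while the paragraph can be read as allowing a next dose. The better reading of the section as a whole is discontinuation, but the paragraph does not say so. This is a minor safety clarification that is worth making.

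**Size.** Per event, the difference is no further infusion against one or more. The number of participants is not given and is likely small. The SAP Section 13 count of participants with an infusion rate reduced to 50% is an upper bound for this course, provided that rate reductions are fully recorded, since a participant must have had the reduced rate to be affected.

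**Limits.** The conclusion assumes that a site may take the paragraph's Grade 2 label at face value; the documents do not show that any site did. The protocol does not define whether a fall from Grade 2 to Grade 1 followed by a return to Grade 2 counts as recurrence, so no claim is made for that course. A reader might also infer a threat to the efficacy conclusions. Nothing supports that: no primary endpoint, alpha or power figure depends on this text.

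**What to change.** Add one sentence to the paragraph below Table 8:

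> This paragraph does not apply to a reaction that meets any Grade 3 or 4 criterion in Table 8, including "recurrence of symptoms following initial improvement"; such reactions require permanent discontinuation.

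No separate rule is needed for residual Grade 1 symptoms that rise to Grade 2. Such a rule would draw a line that the protocol does not contain, and Table 8's own words should govern. If the sponsor does intend re-challenge after recurrence at half rate, Table 8 is the text to change, since the two cannot both stand for that course.

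Cost: a protocol amendment, which under Appendix 2 needs IRB/IEC approval before it is implemented, and notice to approximately 130 centers. Some participants who might have been re-challenged under the paragraph would stop treatment. Data collection and the SAP are unchanged.
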